6.4 Investigational Product Compliance

Single Dose

IP will be administered by the PI or designee on Day 1. Ensure the final IP Otic Solution is administered within the appropriate window of time, depending on the assigned treatment. Refer to the Pharmacy Manual, Section 9.3, for detailed information. Subjects will be provided Ear Care Recommendations (Appendix 12.8) that must be reviewed and acknowledged on Day 1 in the source document. The subject should follow this guidance for the duration of their participation. The investigator will examine the treated ear at every visit.

Multiple Dose

IP will be administered by the PI or designee on Days 1, 15, and 29. Ensure the final IP Otic Solution is administered within the appropriate window of time, depending on the assigned treatment. Refer to the Pharmacy Manual, Section 9.3, for detailed information. Subjects

will be provided Ear Care Recommendations (Appendix 12.8) that must be reviewed and acknowledged at each IP administration visit in the source document. The subject should follow this guidance for the duration of their participation. The investigator will examine the treated ear at every visit.

6.5 Previous and Concomitant Treatment (Medication and Nonmedication Therapy)

These restrictions are required after ASP0598 Otic Solution or placebo administration on Randomization (Day 1), until completion of study procedures at Day 57 (SAD) / Day 85 (single dose expansion or MAD) / Day 113 (multiple dose expansion) or EOS visit.

- Ear drop agents will be used only for the treatment of otitis media with suppurative ear discharge. Only Ciprofloxacin or Ofloxacin ear drops (does not include steroids) are allowed to be used in the ASP0598 Otic Solution or placebo treated ear. Investigators should minimize treatment with ear drops up to a maximum of 10 days and consider alternative treatment (e.g., oral antibiotics).
- Any other topical agents in the ear canal are prohibited to use in the ASP0598 Otic Solution or placebo treated ear.
- Any otologic procedures (e.g., paper patch or surgeries) to the ASP0598 Otic Solution or placebo treated ear are prohibited.

All concomitant medication usage will be noted and recorded during each study visit.

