Decision Process for Dose Escalation and Initiation of MAD

The DEC will decide dose escalation and the initiation and selection of doses for MAD cohorts based on the emerging safety and tolerability data from SAD. After all subjects in a cohort have been dosed and completed study procedures through Day 15, the overall safety and tolerability of the dose will be determined after evaluation of the blinded safety data [treatment emergent adverse events (TEAEs), adverse events (AEs) of special interest, otology examinations (imaging pictures of tympanic membrane, bone conduction hearing at 1, 2, 4 kHz by PTA, TVAS, Modified Brighton Grading Scale), and vital signs] for the current cohort. Cumulative AE data from the preceding cohort(s) will also be included in the assessment for dose escalation. Details will be defined in the DEC Charter.

Dose Escalation Stopping Rules

Depending on the nature, frequency and severity of the safety profile observed in the study, the DEC will decide whether to:

- Proceed with dose escalation and determine the next higher dose or,
- Stop dose escalation (i.e., no further dosing with IP).

Dose escalation will be stopped if 1 (or more) of the following apply:

- If 1 or more subjects in 1 cohort develop cholesteatoma or suspicion of ear neoplasm which is considered to be related to ASP0598.
- If 2 or more subjects in 1 cohort develop Ototoxicity (clinically significant report of vestibular symptoms, tinnitus, or acute hearing loss) which are considered to be related to the IP.
- If 2 or more subjects in 1 cohort develop persistent otitis media or otitis externa unresponsive to oral and topical antibiotics which is described in concomitant treatment requirements section of the synopsis which are considered to be related to the IP.
- If 1 or more subjects in 1 cohort experience AEs of severe intensity or 2 or more subjects in 1 cohort experience AEs of the same character of moderate intensity, which are considered to be related to the IP, and of clinical concern.

In the event that it is deemed relevant to unblind a subject for the purposes of a dose escalation decision, the DEC chair or delegate can request the treatment assigned to one or more from the study statistician. The DEC charter will include information on unblinding of study team members and other details.

Definition of the Maximum Tolerated Dose:

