4.1.1.2 Decision Process for Dose Escalation and MAD Initiation

The DEC will decide dose escalation and the initiation and selection of doses for MAD cohorts based on emerging safety and tolerability data from SAD. After all subjects in a cohort have been dosed and completed study procedures through Day 15, the overall safety and tolerability of the dose will be determined after evaluation of the blinded safety data [treatment emergent adverse events (TEAEs), adverse events (AEs) of special interest, otology examinations (imaging pictures of tympanic membrane, bone conduction hearing at 1, 2, 4 kHz by PTA, TVAS, Modified Brighton Grading Scale, and vital signs] for the current cohort. Cumulative AE data from the preceding cohort(s) will also be included in the assessment for dose escalation. Details will be defined in the DEC Charter.

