4.1.1.3 Dose Escalation Stopping Rules

Depending on the nature, frequency and severity of the safety profile observed in the study, the DEC will decide whether to:

- Proceed with dose escalation and determine the next higher dose or,
- Stop dose escalation (i.e., no further dosing with IP).

Dose escalation will be stopped if 1 (or more) of the following apply:

- If 1 or more subjects in 1 cohort develop cholesteatoma or suspicion of ear neoplasm which is considered to be related to the ASP0598.
- If 2 or more subjects in 1 cohort develop Ototoxicity (clinically significant report of vestibular symptoms, tinnitus, or acute hearing loss) which are considered to be related to the IP.

- If 2 or more subjects in 1 cohort develop persistent otitis media or otitis externa unresponsive to oral and topical antibiotics which is described in concomitant treatment requirements section of the synopsis which are considered to be related to the IP.
- If 1 or more subjects in 1 cohort experience AEs of severe intensity or 2 or more subjects in 1 cohort experience AEs of the same character of moderate intensity, which are considered to be related to the IP, and of clinical concern.

In the event that it is deemed relevant to unblind a subject for the purposes of a dose escalation decision, the DEC chair or designee can request the treatment assigned to one or more subjects from the study statistician. The DEC charter will include information on unblinding of study team members and other details.

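### As worded, the otitis limb of the stopping and discontinuation rules asks for failure of topical antibiotics that Section 6.5 does not allow for otitis externa alone

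*Protocol*

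**What the plan says.** Protocol Section 6.5 limits what may be put in the treated ear: "Ear drop agents will be used only for the treatment of otitis media with suppurative ear discharge". Those drops must be ciprofloxacin or ofloxacin without steroid, for at most 10 days. It continues: "Any other topical agents in the ear canal are prohibited to use in the ASP0598 Otic Solution or placebo treated ear". Investigators are told to keep drop use to a minimum and to "consider alternative treatment (e.g., oral antibiotics"). The Synopsis and Appendix 12.6 carry the same restriction.

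Section 4.1.1.3 stops escalation when two or more subjects in a cohort "develop persistent otitis media or otitis externa unresponsive to oral and topical antibiotics", if the cases are considered related to the product. The Synopsis words it the same way and adds a pointer: "develop persistent otitis media or otitis externa unresponsive to oral and topical antibiotics which is described in concomitant treatment requirements section of the synopsis". The discontinuation criteria use the same two-route test in the Synopsis and in Sections 6.7 and 8.1. They apply only to the multiple ascending dose (MAD) part and the multiple dose expansion. The Synopsis and Section 6.7 refer the reader to Section 6.5; Section 8.1 refers only to an unspecified part of the Synopsis.

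The discontinuation texts also differ in one respect. The Synopsis and Section 6.7 apply the list only when intensity is severe, whereas Section 8.1 sets no such condition.

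**The concern.** The limb names two conditions, otitis media and otitis externa. For one of them, and for part of the other, the protocol forbids the treatment whose failure the limb requires. Otitis externa was clearly meant to be covered. It is named in every version of the limb, and Section 7.3.6 lists it among the adverse events of special interest. The product is also applied through the external auditory canal.

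At stake is whether a rule written to act automatically does so. If a site or the Dose Escalation Committee (DEC) reads the limb literally, persistent otitis externa that has failed oral antibiotics does not count towards the stop. If they read it as covering whichever antibiotics are allowed, it does count. Two careful readers could decide the same case in opposite ways. Giving drops in order to satisfy the limb would be excluded concomitant treatment, which is major deviation PD4 in Section 10.3.

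**Working it through.** The protocol states no rate or operating characteristic for this limb, so there is no figure to reproduce. The check is textual.

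**1. Where the wording stands.** The two-route criterion appears in five places: Synopsis (discontinuation criteria), Synopsis (stopping rules), 4.1.1.3, 6.7 and 8.1. The restriction on drops appears in three: Synopsis, 6.5 and Appendix 12.6. No text makes an exception for otitis externa.

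**2. Can a compliant site meet the limb literally?**

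| Condition in the treated ear | Drops permitted | Oral and topical failure can both be shown |
|---|---|---|
| Otitis media with suppurative discharge, with or without otitis externa | Yes | Yes |
| Otitis media without suppurative discharge | No | No |
| Otitis externa alone | No | No |

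The second row is the lesser one: Section 2.1 describes middle-ear inflammation in this disease as leading to suppurative otitis media.

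**3. Does the cross-reference resolve it?** Four of the five places point to the concomitant-treatment rules, and those rules offer oral antibiotics as an alternative to drops. The reading that only permitted antibiotics count is therefore available, but it is not stated.

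**4. What still stops escalation in the affected cases.** The general limb in 4.1.1.3 requires one severe event, or that "2 or more subjects in 1 cohort experience AEs of the same character of moderate intensity", in either case related and of clinical concern.

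| Two related persistent cases | General limb |
|---|---|
| At least one severe, of clinical concern | Stops |
| Both moderate, same character, of clinical concern | Stops |
| Both mild, or one mild and one moderate | Does not stop |
| Any grade, judged not of clinical concern | Does not stop |

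Only the last two rows depend on the otitis limb. Section 12.4.4 describes mild events as usually transient, so otitis that persists after oral antibiotics would seldom be graded mild.

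**5. What still stops dosing.** The investigator may discontinue for a drug-related event (6.7, 8.1). The investigator must discontinue once continuing is judged against the subject's interest (8.1), and may skip a dose for safety (6.6). The limb's own reach differs by section. Under 8.1 the mandatory rule is lost at any intensity. Under the Synopsis and 6.7 it is lost only for severe cases, because the limb never applied to others there.

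**6. Scope, from planned numbers.** These include placebo and precede any replacement.

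- Escalation: 4 single-dose cohorts × 5 = 20, plus 2 MAD cohorts × 8 = 16, total 36. This takes Section 10.4.1, which gives the DEC escalation decisions in both parts; Section 4.1 mentions only the single-dose part when describing the decision to escalate or stop.
- Discontinuation: 16 in MAD plus up to 39 in the multiple dose expansion, so up to 55. Doses fall on Days 1, 15 and 29, so at most 2 of 3 can be withheld.

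These figures give reach, not expected events. A binomial calculation at an assumed otitis rate would show how often two cases arise in a cohort, not how often a stop is lost, because step 4 removes most of those pairs.

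**The case against.** The strongest reply is that the limb carries its own qualifier. In four of five places the antibiotics are those described in the concomitant-treatment section, and failure of what the protocol allows is a natural reading. This stands as a reason for moderate confidence. It does not settle the matter, because no sentence says it and the pointer in Section 8.1 is too vague to carry it.

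The second reply is that other safeguards leave little uncovered. The general limb is equally mandatory and, for moderate events, uses the same count of two. The DEC also reviews "adverse events (AEs) of special interest, otology examinations" for each cohort, including local reaction grades, and has wide discretion: "Depending on the nature, frequency and severity of the safety profile observed in the study, the DEC will decide whether to" continue or stop. This stands, and it sets the size of the point. The safeguards are not fully equivalent, however. The general limb adds intensity and clinical-concern conditions that the otitis limb lacks, and the rest is judgement.

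A reader might infer that escalation cannot be stopped for otitis externa, or that the whole otitis limb is inoperative. The documents support neither. The general limb and DEC discretion remain, and suppurative otitis media, alone or with otitis externa, can meet the limb as written.

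Finally, Section 4.1.1.2 leaves details to the DEC Charter, which is not among the documents and may define the term. Sites nevertheless apply Sections 6.7 and 8.1 from the protocol itself.

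**Conclusion.** The point holds as a wording conflict with small practical effect. On the literal text, a compliant site cannot meet the otitis limb for otitis externa alone or, less often, for non-suppurative otitis media.

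For escalation, the main loss is the automatic stop for two related persistent cases graded mild or judged not of clinical concern. For dosing, it is the mandatory rule in Section 8.1 and, in the Synopsis and Section 6.7, severe cases only. Adverse event reporting and the efficacy analyses are unaffected.

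The conclusion assumes the literal reading, treatment that complies with Section 6.5, and no overriding definition in the DEC Charter. That persistent otitis would seldom be graded mild is an inference from Section 12.4.4. Confidence is moderate. The correction is worth making because the rule is a mandatory safety rule and the change is nearly free.

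**What to change.** In the Synopsis (both places) and in Sections 4.1.1.3, 6.7 and 8.1, replace the two-route condition with: *unresponsive to oral antibiotics and, where Section 6.5 permits ear drops for the condition, also to topical antibiotics*. In Section 8.1, replace the loose pointer with a reference to Section 6.5. This keeps the two-route test for suppurative otitis media and leaves Section 6.5 and Appendix 12.6 as they are.

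In the same amendment, decide whether discontinuation requires severe intensity, and make the Synopsis, Section 6.7 and Section 8.1 agree. Until that is done, the new phrase makes oral failure sufficient only in the two escalation texts and in Section 8.1. In the Synopsis discontinuation criteria and Section 6.7, the event would still have to be severe.

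The cost is one phrase in five places, one corrected pointer and one reconciliation, with no added visits, subjects or procedures. The limb may fire slightly more often, but only in cases where it literally cannot fire now.

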6.6 Dose Modification

SAD and single dose expansion

Not Applicable.

MAD

On Day 15 or Day 29, treatment can be skipped at the Investigator's discretion based on safety reasons that interrupt IP administration (e.g., ear canal skin irritation, mild otorrhea). Subjects should be encouraged to return to the office for evaluation and additional IP administration within the Day 15 or Day 29 visit windows. In the case that the investigator is unable to conduct IP administration for anything other than safety reasons, consultation with the sponsor may be required.

Multiple dose expansion

The statement above for MAD is also applicable to the multiple dose expansion. Additionally, the treatment on Day 15 or Day 29, treatment will be skipped in cases where complete closure is confirmed. If the perforation is detected on Day 29 after treatment was skipped on Day 15, IP administration can be conducted.

6.7 Criteria for Continuation of Treatment

SAD and single dose expansion

Not applicable because there is a single treatment of ASP0598 Otic Solution or placebo.

MAD and multiple dose expansion

Treatment Discontinuation

During the course of IP administration, if the subject experiences a drug-related AE, the IP administration may be discontinued at the investigator's discretion.

In addition, IP administration will be discontinued if severe intensity occurs in any of the following:

- Subject develops cholesteatoma or suspicion of neoplasm in the treated ear as determined by investigator.
- Subjects develops suspected ototoxicity symptoms (e.g., sudden hearing loss at high frequencies (1, 2, 4 kHz), new high frequency tinnitus or new balance disorder) which are considered by the investigator to be related to the study drug.
- Subjects with persistent otitis media or otitis externa unresponsive to oral and topical antibiotics (as described in Previous Concomitant Treatment [Medication and Nonmedication Therapy of the synopsis and protocol Section [6.5](#)])

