- Investigators may gently remove an obstacle that is blocking the ear canal if it prevents IP application or causes subjects to experience an uncomfortable sensation. If the obstacle is adherent to the tympanic membrane, it should not be removed; it is recommended to wait until the obstacle comes off.
- Subjects should refrain from activities that can increase the middle ear pressure including plane travel (at least 28 days after IP application), positive pressure ventilation (e.g., CPAP or BiPAP) devices, Valsalva maneuvers, excessive high-pressure nose blowing, or diving underwater.
- Subject must refrain from activities that can excessively increase body temperature (e.g. Sauna) for at least 3 days after IP application.
- Subject must refrain from activities that stimulate sweating excessively for at least 3 days after IP application.

Duration of Treatment:

SAD and single dose expansion: Topical application into the affected ear on Day 1.

MAD: Topical application into the affected ear on Days 1, 15, and 29.

Multiple Dose Expansion: Topical application into the affected ear on Day 1 and if the subject has not achieved complete closure of the TMP at Day 15 and Day 29, additional treatment will occur. If the subject achieves complete closure on either Day 15 or Day 29, no additional treatment is required at those visit(s).

Treatment Discontinuation Criteria:

SAD and single dose expansion

Not applicable because there is a single treatment of ASP0598 Otic Solution or placebo.

MAD and multiple dose expansion

Treatment Discontinuation

During the course of IP administration, if the subject experiences a drug-related adverse event (AE), the IP administration may be discontinued at the investigator's discretion.

In addition, IP administration will be discontinued if severe intensity occurs in any of the following situations:

- Subject develops cholesteatoma or suspicion of neoplasm in the treated ear as determined by the investigator.
- Subject develops suspected ototoxicity symptoms (e.g., sudden hearing loss at high frequencies (1, 2, 4 kHz), new high frequency tinnitus or new balance disorder) which are considered by the investigator to be related to the study drug.
- Subjects with persistent otitis media or otitis externa unresponsive to oral and topical antibiotics (as described in Previous and Concomitant Treatment [Medication and Nonmedication Therapy of the synopsis and protocol Section 6.5])

Dose Escalation:

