8 DISCONTINUATION

8.1 Discontinuation of Individual Subject(s) From Study Treatment

SAD and single dose expansion

Not applicable because there is a single treatment of ASP0598 Otic Solution or placebo.

MAD and multiple dose expansion

Treatment Discontinuation

During the course of IP administration, if the subject experiences a drug-related adverse event (AE) the IP administration may be discontinued at the investigator's discretion.

In addition, study drug administration will be discontinued if any of the following occur:

- Subject develops cholesteatoma or suspicion of neoplasm in the treated ear as determined by investigator.
- Subjects develops suspected ototoxicity symptoms (e.g., sudden hearing loss at high frequencies (1, 2, 4 kHz), new high frequency tinnitus or new balance disorder) which are considered by the investigator to be related to the study drug.

- Subjects with persistent otitis media or otitis externa unresponsive to oral and topical antibiotics (as described in other area of synopsis)

A discontinuation from treatment is defined as a subject who enrolled in the study and for whom study treatment is permanently discontinued for any reason.

The subject is free to withdraw from the study treatment and/or study for any reason and at any time without giving reason for doing so and without penalty or prejudice. The investigator is also free to discontinue the subject from study treatment or to terminate a subject's involvement in the study at any time if the subject's clinical condition warrants it.

The reason for discontinuation from study treatment must be documented in the subject's medical records.

A subject must discontinue study treatment for any of the following reasons:

- Subject requests to stop treatment.
- Any clinical AE, laboratory abnormality or intercurrent illness, in the opinion of the investigator, indicates continued treatment is not in the best interest of the subject.

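### For multiple dosing, the synopsis and section 6.7 make the IP stop mandatory for three ear events only when severe; section 8.1 makes it mandatory at any severity, and no text says which governs.

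*Protocol*

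**What the plan says.** The rule for stopping IP in MAD and multiple dose expansion appears in three places in the protocol.

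- **Synopsis, Treatment Discontinuation Criteria:** "In addition, IP administration will be discontinued if severe intensity occurs in any of the following situations".
- **Section 6.7:** "In addition, IP administration will be discontinued if severe intensity occurs in any of the following".
- **Section 8.1:** "In addition, study drug administration will be discontinued if any of the following occur".

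Each lead-in is followed by the same three events: cholesteatoma or a suspected neoplasm in the treated ear; suspected ototoxicity that the investigator attributes to study drug; and persistent otitis media or externa that antibiotics have not resolved.

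The stopping rules in the synopsis and 6.7 do not cite 8.1. Section 8.1 points back only in its otitis item, and only loosely: "Subjects with persistent otitis media or otitis externa unresponsive to oral and topical antibiotics (as described in other area of synopsis".

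The default schedule is in 6.4: "IP will be administered by the PI or designee on Days 1, 15, and 29". SAD and single dose expansion are unaffected, because there is only one dose.

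**The concern.** A mandatory safety stop needs one trigger. Here the same event, at mild or moderate severity, must end dosing under 8.1 but does not have to under 6.7 or the synopsis. Section 6.7 is headed as the criteria for continuing treatment and comes directly after the dose-modification section, so it is where a site deciding about the Day 15 or Day 29 dose would naturally look. It carries the narrower trigger.

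At stake is further exposure, in a first-in-human study (2.2), after an event that one section treats as the end of dosing. The three event types also fall within the adverse events of special interest, whose incidence is a primary endpoint (3.1, 7.3.6). No claim is made about power or type I error.

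**Working it through.** The plan gives no figure to reproduce. The check is a comparison of texts, followed by simple dose arithmetic.

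**1. What differs**

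| Element | Synopsis | 6.7 | 8.1 |
|---|---|---|---|
| Study parts | MAD, multiple dose expansion | same | same |
| Cholesteatoma or suspected neoplasm | listed | listed | listed |
| Ototoxicity, must be judged drug-related | listed | listed | listed |
| Otitis, must be persistent and unresponsive | listed | listed | listed |
| Severity needed for a mandatory stop | severe | severe | none |

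The qualifiers inside each item match, so severity is the only substantive difference. Neither the rest of the protocol, nor its amendment summary, nor the SAP sets an order of precedence.

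**2. Can a listed event be non-severe?** Section 12.4.4 grades severity by effect on daily activities, effect on clinical status and need for intensive treatment. A suspected neoplasm or an early cholesteatoma could be graded mild or moderate, so the condition can change the decision.

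**3. What else would stop or delay dosing after a non-severe listed event**

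- *Discretionary stop (6.7).* Available for a drug-related AE. It covers every listed ototoxicity event, because relatedness is part of that item. It does not cover cholesteatoma, neoplasm or otitis judged unrelated.
- *Best-interest stop (8.1).* Mandatory when an AE, "in the opinion of the investigator, indicates continued treatment is not in the best interest of the subject". It rests on judgement.
- *Dose skipping (6.6).* Allowed "based on safety reasons that interrupt IP administration (e.g., ear canal skin irritation, mild otorrhea". It omits or delays a dose and does not end dosing.
- *Escalation stopping rules (4.1.1.3).* One related cholesteatoma or suspected neoplasm in a cohort, or two related cases of ototoxicity or of unresponsive otitis, stops escalation. That section equates stopping with no further IP dosing. None of these three triggers has a severity condition. They apply to related events, act through the Dose Escalation Committee, and reach MAD (10.4.1) but not multiple dose expansion.

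Each provision narrows the gap. Together they still leave, for example, a non-severe event judged unrelated in multiple dose expansion, where only investigator judgement or a skipped dose applies.

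**4. Maximum extra exposure per subject**

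Inputs: volume 0.15 mL; planned multiple-dose concentrations 5 and 15 µg/mL (Table 6, which allows them to be adapted); dosing on Days 1, 15 and 29.

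Dose per administration = concentration × volume:

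- 5 × 0.15 = 0.75 µg
- 15 × 0.15 = 2.25 µg

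| Listed event occurs | Further doses, at most | At 5 µg/mL | At 15 µg/mL |
|---|---|---|---|
| Before the Day 15 dose | 2 | 2 × 0.75 = 1.5 µg | 2 × 2.25 = 4.5 µg |
| Between the Day 15 and Day 29 doses | 1 | 0.75 µg | 2.25 µg |
| After the Day 29 dose | 0 | 0 | 0 |

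These amounts are for subjects on active treatment.

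**5. Subjects under the rule**

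- MAD: 2 × 8 = 16, of whom 2 × 6 = 12 active.
- Multiple dose expansion, if opened: up to 3 × 13 = 39, of whom 2 × 13 = 26 active.

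**6. Nonclinical margin.** The repeat-dose NOAEL, for three doses at 2-week intervals in mice and cynomolgus monkeys, was 150 µg/mL (2.1.1). 150 / 15 = 10.

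**The case against.** The strongest reply is that the rules are cumulative. The synopsis and 6.7 require a stop for severe events and are silent on the rest; 8.1, the section on discontinuation from treatment, requires more. An investigator who follows 8.1 complies with all three, and 10.3 makes the investigator responsible for following the protocol. This stands as far as it goes. A reader might infer that 6.7 authorises dosing after a milder event, or that a site cannot comply with all three texts. The documents support neither. But a general duty to follow the protocol does not cure a section on continuing treatment that states a narrower trigger and does not point to the wider one.

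A second reply is that the non-severe gap may be small, since a suspected neoplasm or sudden hearing loss could well be graded severe. That is fair. The documents allow neither a count of non-severe events nor a claim that there would be none.

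A third is that the more protective wording is a preference, because two of the three texts carry the severity condition. It is true that intent cannot be read from the text, so the fix leaves room for a justified severe-only rule.

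It is also tempting to work out the latest day on which otitis treatment could start and still leave a dose to come, using "Investigators should minimize treatment with ear drops up to a maximum of 10 days" from 6.5. The documents do not support such limits. That cap concerns drops permitted only for otitis media with suppurative discharge; no course length is set for calling otitis unresponsive; and MAD visits may move by 3 days either way. All that can be said is that otitis must first fail treatment, which shortens its window.

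**Conclusion.** The inconsistency is real and should be corrected. For the same three events in the same study parts, two texts make the stop mandatory only at severe intensity, one makes it mandatory at any severity, and nothing sets precedence. Confidence in the textual difference is high; its practical effect cannot be quantified beyond the per-subject ceiling.

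That ceiling is 2 further doses, or 1.5 µg at 5 µg/mL and 4.5 µg at 15 µg/mL. It assumes the planned concentrations are used, including in multiple dose expansion, where the dose is chosen at interim; that the event precedes the Day 15 dose; and that the site acts on 6.7 or the synopsis alone.

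A reader might infer that subjects are likely to be harmed. The documents do not show this: the number of events is unknown, several provisions narrow the gap, and the repeat-dose NOAEL is 10 times the highest planned concentration. Further exposure is the only consequence claimed.

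**What to change.** Delete the severe-intensity condition from the lead-ins in the synopsis and 6.7, so that both use the trigger in 8.1. State the rule once, in 8.1, and cross-reference it from the other two places. This direction is preferred because 8.1 is the more protective rule and already requires these stops. If the sponsor intended a severe-only rule, it should justify that and amend 8.1 instead, so that one trigger applies throughout.

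The cost is a clarifying amendment signed by sponsor and investigator, with written verification of IRB/IEC approval before implementation (12.1.3), and notice to sites. No procedures are added.

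The downside is possibly a few more early IP stops. These subjects remain in follow-up under 8.2. In multiple dose expansion, however, the protocol counts treatment discontinuation for any reason as an intercurrent event (3.2.1). Under 3.2.3, closure status would be carried forward from before the stop and later size measurements would be left out of the MMRM. With 13 subjects per group, even a few stops could matter. SAP 5.3.1 lists discontinuation from the study's investigational period rather than from treatment, so this cost follows from the protocol's definition and the SAP's list would not produce it.
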